dexmedetomidine infusion.[12, 13] It is reasonable to postulate that the anti-inflammatory properties of ketamine as revealed by decreased levels of the inflammatory marker IL-6 may be associated with a decrease in postoperative renal dysfunction.

Patient age (> 65 years) and increased surgical complexity (with longer operative times) are known risk factors for postoperative cognitive dysfunction, delirium, and renal dysfunction.[14-16] These higher risk patients would be the population that would benefit most from the potential decrease in these important areas of morbidity.

Specific Aims/Hypotheses:

We aim to determine the impact of ketamine administration at induction of anesthesia on delirium, postoperative cognitive dysfunction, renal dysfunction, intra and postoperative hemodynamics, requirement for inotropic and vasopressor support, and postoperative mortality.

Specific Aim 1: 1. Determine the incidence of cognitive dysfunction and delirium in patients who receive ketamine for induction compared with those who receive propofol.

Specific Aim 2: Determine the impact of ketamine on patient hemodynamics as well as the dose of vasopressor and inotropes used during the intra and postoperative periods.

Specific Aim 3: Determine the incidence of renal dysfunction, defined by AKIN criteria, in patients who receive ketamine for induction compared with those who receive propofol.

STUDY DESIGN

We propose a prospective study in which patients will be randomized for induction with ketamine versus propofol (another regularly used anesthesia induction agent). Hemodynamics before, during and after cardiopulmonary bypass and use of inotropic and vasopressor medications will be recorded as per usual charting. The incidence of delirium, cognitive dysfunction, and renal dysfunction will be compared between the ketamine and propofol groups.

Inclusion/Exclusion Criteria

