We will include patients age greater than or equal to 70 years presenting for cardiac surgery at the Mayo Clinic in Rochester, Minnesota. Patients will be eligible for inclusion if they are schedule to undergo complex cardiac surgery. Complex cardiac surgery will be defined as surgery involving more than one heart valve, redo-sternotomy procedures, or combined valvular and CABG procedures. Exclusion criteria will include left or right ventricular assist device implantation or explantation, procedures not requiring cardiopulmonary bypass, active infection or sepsis, severe hepatic disease or ascites, pre-operative renal dysfunction including a baseline creatinine equal to or greater than 2.0 mg/dL or requiring dialysis, immunosuppressive medication use (including steroid use), immunodeficiency syndrome, known neurologic or psychiatric disorder, or use of drugs for psychosis.

Number of Subjects

The incidence of renal dysfunction in patients following cardiac surgery has been reported to be anywhere from 21% to 38%.[13, 17, 18] The incidence of delirium after cardiac surgery has been reported over a broad range including 18% to 31%.[2, 14] Assuming a reduction in the incidence of renal dysfunction and delirium of approximately 10%, an appropriate sample size would be approximately 20 patients per group. We will plan to recruit 26 patients in each group.

Randomization and Consent

Written, informed consent will be obtained. The study will be minimal risk and non-invasive. Ketamine and propofol are both standard and commonly used medications for the induction of anesthesia. All aspects of care will be as per usual for patients undergoing these operations at The Mayo Clinic. Subjects will be recruited by letter via review of the surgical listing and scheduled for a preoperative appointment to review the study and obtain consent. Randomization will occur via delivery of a sealed envelope by a member of the study staff who is not directly involved with patient care on the morning of surgery to the consultant anesthesiologist assigning the patient to the ketamine or propofol group.

Human Subjects

Detailed Description: The human subjects will be prospectively studied after being randomized to receive one of two commonly used anesthesia induction agents.

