Population: The subject population in this study will include all patients admitted to Mayo Clinic Rochester for cardiac surgery that meet the inclusion criteria. No specific populations (regardless of race, ethnicity or gender) will be excluded from this study aside from those who meet the exclusion criteria described above.

Research Materials: Electronic data will be stored securely and only accessed by those authorized on the IRB application.

The study will be minimal risk and written, informed consent will be obtained.

Potential Risks: This study compares two commonly used anesthetic agents. This study will not increase the risk of physical harm beyond what the surgical procedure naturally carries. The only potential risk is a breach of confidentiality, but this is thoroughly addressed as described below.

Protection: Data will be collected and stored on a secure Mayo server in a password-locked folder. No patient names will be stored, and the only identifiers included in the data will be clinic number, date of birth and date of admission. Only investigators authorized by the IRB will be allowed access to the study data.

Protocol/Methods

After written, informed consent is obtained the following baseline cognitive function studies will be administered by the anesthesia clinical research unit: Trail-making test, the Mini-Mental State Examination, Hopkins Verbal Learning Test (Revised forms 1 and 2), Digit Span forward and backward, Controlled Oral Word Association, and Stroop Test.

Anesthetic management will be directed by the consultant anesthesiologist as per routine aside from the following: Patients will be randomized to ketamine (1-2 mg/kg) versus propofol (0.5-1 mg/kg) induction with additional medication administered as needed to achieve intubating conditions. Inhalation anesthetic for induction in

combination with either propofol or ketamine will be permitted. The ketamine group will not receive propofol and vice versus. Maximum fentanyl bolus dosing will be 10 µg/kg, consistent with the currently implemented cardiac surgery rapid recovery protocol. Albumin administration will be avoided, but ultimately left to the discretion of the consultant anesthesiologist. Invasive monitoring techniques will be left to the discretion of the consultant anesthesiologist as per routine.

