All other aspects of patient care will be as per routine including administration of inotropic or vasopressors as needed at the discretion of the anesthesiologist and /or cardiac surgical team. Administration of inotropic or vasopressors will be recorded in the anesthesia record as per usual practice. Propofol or dexmedetomidine infusions will be utilized for sedation at the end of the procedure as per usual practice.

The Confusion Assessment method for the ICU (CAM ICU) score will be recorded every 12 hours in the ICU as per routine. After dismissal from the ICU, a CAM score will be reviewed until hospital discharge. Prior to hospital discharge or within 1- 2 days prior to discharge, the patient will undergo post-intervention cognitive function studies administered by the anesthesia clinical research unit: Trail-making test, the Mini-Mental State Examination, Hopkins Verbal Learning Test (Revised forms 1 and 2), Digit Span forward and backward, Controlled Oral Word Association, and Stroop Test.

Outcome measurements

After inclusion in the study, demographic and medical data from all patients including age, height, weight, medical co-morbidities and current medications will be recorded and saved in the database. In addition, information regarding the planned procedure and the specifics of each patient's cardiac disease including ventricular

function, current cardiac anatomy and details of previous cardiac repairs will be recorded. Liver and renal function will be assessed by recording liver function tests and renal indices if available in the preoperative medication record.

Our primary outcomes will be the incidence of cognitive dysfunction and delirium as well as the incidence of renal dysfunction. Secondary outcomes will include assessing differences in hemodynamics, inotropic use and vasopressor use between the ketamine and propofol group. Mortality during admission for cardiac surgery will be assessed, however, the study will not be powered for this to be a primary outcome measure.

Data Analysis

Incidence of renal and cognitive dysfunction and delirium will be expressed as a percentage. Values will be compared between ketamine and non-ketamine groups using *t*-tests and ANOVA. A *P* value of less than 0.05 will be considered significant. Secondary outcomes will be analyzed using a *t*-test or ANOVA. All comparisons will be completed adjusting for multiple comparisons using the Bonferroni method.

References

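### The delirium comparison leaves out age and baseline cognition, both known before assignment: prespecified adjustment would be a cheap improvement, not the repair of an error

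*Combined protocol and SAP*

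**What the plan says.** Outcome measurements states: "Our primary outcomes will be the incidence of cognitive dysfunction and delirium as well as the incidence of renal dysfunction". Delirium is therefore one of three primary incidences.

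Data Analysis gives the comparison in one sentence, "Values will be compared between ketamine and non-ketamine groups using" t-tests and ANOVA. The threshold is a P "value of less than 0.05 will be considered significant". The only adjustment is for multiplicity: "All comparisons will be completed adjusting for multiple comparisons using the Bonferroni method". No baseline covariate appears.

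Three other sections bear on this:
- **Background and Significance**, closing paragraph: "Patient age (> 65 years) and increased surgical complexity (with longer operative times) are known risk factors" for all three primary outcomes.
- **Outcome measurements**: the database will hold "demographic and medical data from all patients including age".
- **Protocol/Methods**: once consent is given, "the following baseline cognitive function studies will be administered by the anesthesia clinical research unit". The battery includes the Mini-Mental State Examination (MMSE).

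Under Randomization and Consent, consent is taken at a preoperative visit and the allocation envelope is delivered on the day of the operation. Baseline cognition therefore precedes assignment. That section mentions neither stratification nor blocking. Number of Subjects sets 26 patients per arm.

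**The concern.** With 26 patients per arm, the arms can differ by chance in age and baseline cognition. If these predict delirium, the raw difference in percentages carries part of that imbalance. The plan calls one of them a risk factor and collects both, yet uses neither in the design or the analysis.

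Two things are at stake. One is some precision. The other is how the single realised trial can be read if its baseline table looks uneven: an adjustment chosen at that stage would look driven by the data, whereas one fixed in advance would not.

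**Working it through.** **The plan's own figure.** The plan gives no figure for covariate adjustment. Its nearest figure is about 20 per group for a reduction of about 10%, and this does not reproduce. For 31% to 21%, two-sided 5%, 80% power (sidedness and power are assumed, as neither is stated): n = [1.96·√(2·0.26·0.74) + 0.842·√(0.31·0.69 + 0.21·0.79)]² / 0.10² ≈ 301 per group. At 26 per group the power is 12.6%. That is a separate matter, but it explains why adjustment cannot do much for power here.

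**Inputs.** From Number of Subjects: 26 per arm, and delirium rates of 18% and 31%. Assumed: one standardised baseline risk index (age and cognition combined) with an odds ratio (OR) of 1.5, 2 or 3 per SD in a logistic model.

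**Step 1, size of chance imbalance.** The SD of the between-arm difference in the index is √(2/26) = 0.277. An imbalance of at least 0.4 SD has probability 2·[1 − Φ(0.4/0.277)] = 2·[1 − Φ(1.442)] = 14.9%. Its mean absolute size in those trials is 0.277·φ(1.442)/[1 − Φ(1.442)] = 0.277·0.141/0.0746 ≈ 0.52 SD.

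**Step 2, shift in the raw risk difference.** Shift = slope × 0.52, where the slope is the change in delirium risk per SD of the index. R² = slope²/[p(1 − p)].

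| Delirium rate | OR per SD | Slope | R² | Mean shift |
|---|---|---|---|---|
| 31% | 1.5 | 0.084 | 0.033 | 4 points |
| 31% | 2 | 0.135 | 0.085 | 7 points |
| 31% | 3 | 0.191 | 0.171 | 10 points |
| 18% | 1.5 | 0.058 | 0.023 | 3 points |
| 18% | 2 | 0.095 | 0.061 | 5 points |
| 18% | 3 | 0.137 | 0.128 | 7 points |

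Simulation (20,000 or more trials per setting) gives the same shifts for the raw estimate and under 0.5 point for the adjusted one.

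**Step 3, variance.** With q covariates and 52 patients, the ratio of adjusted to raw variance is about (1 − R²)·[1 + q/(52 − q − 3)], with equal rates in both arms.
- One index (factor 1 + 1/48 = 1.021). OR 2 at 18%: 0.939·1.021 = 0.96. OR 3 at 31%: 0.829·1.021 = 0.85 (simulated 0.84 to 0.85). OR 1.5: 0.99 to 1.00.
- Two covariates (factor 1 + 2/47 = 1.043). OR 2 at 18%: 0.98. OR 3 at 31%: 0.86. OR 1.5: 1.01 to 1.02. No prognostic value: 1.04, and up to 1.05 in simulation.

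**Step 4, error rate and power at two-sided 5%.** Over all trials, a true null is rejected in 5.4 to 5.8% raw and 5.0 to 5.3% adjusted. Power with one covariate, OR 1.5 to 3:
- 31% to 21%: 13.5 to 13.8% raw, 12.9 to 14.1% adjusted.
- 18% to 8%: 19.3 to 19.6% raw, 18.2 to 19.1% adjusted.

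With two covariates, the loss reaches about 2 points at worst.

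**Step 5, events.** For 18% against 8%, the expected total is 26·0.18 + 26·0.08 = 6.8. For 31% against 21% it is 26·0.31 + 26·0.21 = 13.5.

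**The case against.** The strongest reply is that nothing is invalid. Randomization makes the raw comparison unbiased, and its standard error already allows for chance imbalance, as the overall rejection rate in step 4 shows. This stands, and it rules out two stronger readings.

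- **A reader might infer that the raw test is biased or has an inflated error rate.** It does not. Rejection rises only among trials already selected for imbalance of at least 0.4 SD: to about 8 to 12% at OR 2 to 3 and 31% delirium, at the 5% level. The plan's Bonferroni correction lowers this further. At 0.05/3 (taking the three primary outcomes as the family, an assumption) it is in the region of 3 to 4%, against a nominal 1.7%.
- **A reader might infer that imbalance could mimic or cancel the assumed effect.** Reading the planned reduction as 10 points, the chance that imbalance in this index alone moves the result that far is below 0.01% at OR 1.5, 0.02 to 0.7% at OR 2, and 0.9 to 5.9% at OR 3. Ordinary sampling noise (SD 0.107 to 0.128) gives a difference of 10 points or more in 35 to 44% of null trials, and adjustment leaves most of that. At 31% and OR 3, the 95% half-width falls only from 1.96·0.129 = 25 points to 1.96·0.118 = 23 points.

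The prognostic premise is also partly outside the documents. The named risk factor is age above 65, and every patient is at least 70, so nothing shows how strongly age predicts within this range, though no upper age limit is set. The documents do not call baseline cognition a delirium risk factor, and known neurologic or psychiatric disorder is excluded. This stands and keeps the odds ratios as assumptions.

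Finally, the sample-size statement and the use of a t-test for an incidence are larger problems. They are separate, and solving them would leave this point as it is.

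**Conclusion.** The point holds as a recommendation of moderate weight, not as a defect in validity. The plan omits baseline values that it will already have, one of which it calls prognostic. The benefit is protection from imbalance in the roughly one trial in seven where it is appreciable, plus a modest gain in precision if the covariates are reasonably predictive. If they are weak, there is no gain and a small loss. Power is no reason to make the change. All sizes rest on the assumed odds ratios of 1.5 to 3 per SD, delirium rates of 18 to 31%, complete data on 26 patients per arm, and a two-sided 5% test unless stated otherwise.

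**What to change.** In Data Analysis, prespecify one linear model for delirium (yes/no) with arm, age and baseline MMSE score, both covariates continuous. Report the adjusted risk difference with a confidence interval at the planned Bonferroni-adjusted level, and show the raw percentages by arm alongside. State the number of comparisons that sets that level.

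Use the linear model and not a logistic fit: with as few as about 7 events, arm plus two covariates would be fragile on the logistic scale. For the same reason, add no further covariates. Since a two-group t-test is already a linear model with arm alone, this extends the planned method by two terms. Add age to the models for cognitive dysfunction and renal dysfunction, because the plan names it for all three primary outcomes.

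The cost is a few lines of text and no new data. It uses one or two degrees of freedom, with slightly lower precision and power if the covariates turn out to be weak.

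### Repeated haemodynamic values are to be compared by t-test or ANOVA with no baseline covariate and no stated patient-level unit of analysis, which loses precision and leaves an invalid pooled analysis open

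*Combined protocol and SAP*

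**What the plan says.** Specific Aim 2 is to "Determine the impact of ketamine on patient hemodynamics as well as the dose of vasopressor and inotropes used" during and after the operation. The Study Design section describes the data: "Hemodynamics before, during and after cardiopulmonary bypass and use of inotropic and vasopressor medications will be recorded as per usual charting". The Outcome measurements section makes these secondary: "Secondary outcomes will include assessing differences in hemodynamics, inotropic use and vasopressor use between the ketamine and propofol group".

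The Data Analysis section gives the method in one sentence, which begins "Secondary outcomes will be analyzed using a" and names a t-test or ANOVA. It sets the threshold as a P "value of less than 0.05 will be considered significant" and adds: "All comparisons will be completed adjusting for multiple comparisons using the Bonferroni method". The sample size is in Number of Subjects: "We will plan to recruit 26 patients in each group".

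The plan does not name the haemodynamic variables, the number or timing of readings, a summary value per patient, a baseline covariate, a repeated-measures or random-effects term, or the number of comparisons that Bonferroni covers. It gives no SD, effect size or power for these outcomes.

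**The concern.** Readings from one patient at different phases are correlated. A two-group t-test or one-way ANOVA assumes independent observations, so it is valid here only if each patient enters once per test. The plan does not say that each patient does.

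A second loss does not depend on how that gap is filled. A patient's haemodynamics before induction usually predict the later values. With 52 patients, removing that predictable part of the variation is the cheapest precision available, and neither named test does so. Aim 2 is one of three specific aims, so an inconclusive result there, or a false positive from pooled readings, would matter to the report even though the outcomes are secondary.

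**Working it through.** The plan has no figure for these outcomes to reproduce, so what follows shows sizes under stated assumptions.

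**Inputs.** From the documents: n = 26 per arm, alpha 0.05 (taken as two-sided), and at least three phases. Assumed: m = 3 readings after induction; a true difference of 0.6 SD at every phase; the same correlation ρ between any two readings of a patient, including the pre-induction reading; ρ = 0.3 to 0.7.

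**1. Charitable reading: one mean per patient.** In units of the single-reading SD, the variance of a three-reading mean is (1 + 2ρ)/3. Adjusting for the pre-induction value removes ρ², leaving (1 + 2ρ)/3 − ρ². The standardised difference is d = 0.6/√variance. Power is taken from the non-central t with non-centrality d·√(26/2) and 50 degrees of freedom (49 with the covariate).

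| ρ | Variance, unadjusted | d | Power | Variance, adjusted | d | Power |
|---|---|---|---|---|---|---|
| 0.3 | 0.533 | 0.822 | 83% | 0.443 | 0.901 | 89% |
| 0.5 | 0.667 | 0.735 | 74% | 0.417 | 0.930 | 91% |
| 0.7 | 0.800 | 0.671 | 66% | 0.310 | 1.078 | 97% |

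With complete data, the arm test in a repeated-measures ANOVA is the same comparison of per-patient means, so the unadjusted column covers it too. In 20,000 simulated trials per setting, the unadjusted mean kept a type I error of 4.8% to 5.2%.

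**2. The same comparison under Bonferroni.** If three variables shared the 0.05 (an assumption), each would be tested at 0.05/3. Power would then be 57% unadjusted and 80% adjusted at ρ = 0.5, and 48% and 92% at ρ = 0.7. The gain does not come from relaxing alpha.

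**3. A weaker baseline.** If the pre-induction value correlates only 0.3 with later readings while those correlate 0.5 with each other, the adjusted variance is 0.667 − 0.09 = 0.577 and power is 80%, against 74% unadjusted. With 0.7 between later readings, it is 0.800 − 0.09 = 0.710 and 71%, against 66%.

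**4. Raw readings pooled as independent.** The true variance of the arm difference is 1 + (m − 1)ρ times the one assumed. Type I error is 2·[1 − Φ(1.96/√(1 + 2ρ))].

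| ρ | 1 + 2ρ | 1.96/√(1 + 2ρ) | Type I error | Simulated |
|---|---|---|---|---|
| 0.3 | 1.6 | 1.550 | 12.1% | 12.5% |
| 0.5 | 2.0 | 1.386 | 16.6% | 16.5% |
| 0.7 | 2.4 | 1.265 | 20.6% | 20.5% |

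Bonferroni over three variables does not repair this: the rate per test is 5.8% to 12.2%, not 1.67%.

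**5. Overall test or test by phase.** If the 0.6 SD difference exists in one of three phases only, the mean differs by 0.6/3 = 0.2 SD. An overall test then has 12% to 16% power unadjusted and 19% to 25% adjusted (ρ = 0.3 to 0.7). The chance that at least one of three unadjusted per-phase tests succeeds at 0.05/3 is 39% to 40% by simulation.

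**The case against.** The strongest reply is that this is a gap in specification and that the plan commits to no wrong method. ANOVA can mean repeated-measures ANOVA, and a t-test can be run on one mean per patient. Both fit the text and keep the error rate at 5%. That stands. A reader might infer that the plan can only be followed badly, or that its type I error is 12% to 21%. The documents do not support either inference, because nowhere do they say that raw readings will be pooled.

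Omitting baseline in a randomised comparison makes the standard error larger, not wrong. That stands as well; the baseline point concerns power alone.

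A power gain can be overstated by setting a per-phase test at 0.05/3 (38% for 0.6 SD) against one baseline-adjusted test of a single value at 0.05 (69% at ρ = 0.5, 84% at 0.7). At 0.05/3 those adjusted figures are 51% and 71%. The comparisons in the working hold alpha and the summary measure fixed.

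A single overall arm test is no free improvement either, since it performs poorly when the effect is confined to one phase. The documents do not say which question Aim 2 asks.

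Finally, no pre-induction haemodynamic value is named, and a reading before bypass may already follow induction. This limits the remedy to a value truly taken before the study drug.

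**Conclusion.** The point holds for haemodynamics. Even on the most favourable reading, the stated analysis gives up precision that a pre-induction covariate would recover. For 0.6 SD over three phases with 26 per arm, power rises from about 74% to 91% at correlation 0.5 and from 66% to 97% at 0.7. The gain is smaller, about 5 to 6 points, where the baseline correlation is only 0.3. The effect size, number of readings and correlations are assumptions, because the plan supplies none. Inflation to 12% to 21% is a conditional risk that the wording leaves open.

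A reader might extend the point to vasopressor and inotrope doses. The documents do not support that: they describe no pre-treatment dose, and one total per patient has no within-patient correlation to ignore. Nor do they show that a rank test is needed for doses. Without dose data, that choice is a trade-off resting on assumed distributions.

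These are secondary outcomes, so this is a worthwhile improvement and does not threaten the primary comparison.

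**What to change.** In Data Analysis, name each haemodynamic variable and its time points. For each, replace the t-test or ANOVA with one of two analyses:

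- ANCOVA on a defined per-patient summary of the post-induction readings, with arm and the pre-induction value as terms; or
- a mixed model with a patient random effect, arm, phase and the pre-induction value.

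Do not adjust for any value taken after induction, because the study drug may already have affected it. State before the data are examined whether the arm effect is tested overall or by phase; that choice is the sponsor's. Keep Bonferroni across variables, and across phases if testing is by phase, and state the number of comparisons it covers.

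The cost is a few sentences and slightly more programming, with no added patients or visits. The change relies on pre-induction values being part of usual charting, which is assumed here and should be confirmed. If they are not charted, the precision gain is unavailable, but the patient should still be the unit of analysis.

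### Bonferroni is applied to all comparisons with no family or divisor, so the threshold for the three primary outcomes is not fixed and, on the plain reading, shrinks with every secondary test

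*Combined protocol and SAP*

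**What the plan says.** All references are to the combined protocol and SAP.

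- **Outcome measurements** names three primary outcomes: "Our primary outcomes will be the incidence of cognitive dysfunction and delirium as well as the incidence of renal dysfunction". It then names three secondary domains: "Secondary outcomes will include assessing differences in hemodynamics, inotropic use and vasopressor use between the ketamine and propofol group". In-hospital mortality is also to be assessed, with the remark that the study is not powered for it.
- **Data Analysis** sets one criterion, that a P "value of less than 0.05 will be considered significant". It continues "Secondary outcomes will be analyzed using a *t*-test or ANOVA", and the next sentence is "All comparisons will be completed adjusting for multiple comparisons using the Bonferroni method".
- **The number of secondary comparisons is open.** Study Design says "Hemodynamics before, during and after cardiopulmonary bypass and use of inotropic and vasopressor medications will be recorded as per usual charting", and Specific Aim 2 refers to the "dose of vasopressor and inotropes used during the intra and postoperative periods". No variables or time points are listed.
- **Cognitive dysfunction** is named as an incidence. Protocol/Methods gives a battery of six instruments ("Trail-making test, the Mini-Mental State Examination, Hopkins Verbal Learning Test (Revised forms 1 and 2), Digit Span forward and backward", then word association and Stroop) and no rule for classing a patient as having dysfunction.
- **Number of Subjects** plans 26 per group and mentions no adjusted alpha.

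Nowhere does the document state which tests form the family, how many there are, what the per-test threshold is, or whether the 0.05 applies before or after adjustment.

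**The concern.** Bonferroni is a decision rule only once the divisor is known, and here it cannot be recovered from the text. Because the sentence covers every comparison and directly follows the one on secondary outcomes, the plain reading puts primary and secondary tests in one family. Each haemodynamic or drug-use comparison then lowers the threshold for delirium, cognitive dysfunction and renal dysfunction.

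Two things are at stake. The primaries may lose power to tests that were never meant to compete with them. And if the count is settled only at analysis, a borderline primary result can be made significant or not by the choice of divisor.

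**Working it through.** **Inputs.** Nominal alpha 0.05 (Data Analysis). Three primaries, three secondary domains and mortality (Outcome measurements). 26 per arm (Number of Subjects). Control rates 21–38% for renal dysfunction and 18–31% for delirium, with a reduction of about 10% (Number of Subjects). Delirium 31% vs 3% in one earlier study (Background and Significance). Assumed: two-sided tests, 10% read as percentage points, and 20 tests as an illustration of a longer secondary list.

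**Step 1. The plan's own figure.** There is no adjusted alpha to reproduce. The figure of about 20 per group does not reproduce either. With the usual two-proportion formula (pooled variance, two-sided 0.05, 80% power assumed), a 10-point reduction needs 177 per arm (18% to 8%) to 346 per arm (38% to 28%).

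**Step 2. Thresholds.** Per-test alpha = 0.05/m.

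| m | What is counted | Threshold |
|---|---|---|
| 3 | primaries only | 0.0167 |
| 6 | plus three secondary domains, one test each | 0.0083 |
| 7 | plus mortality | 0.0071 |
| 20 | assumed | 0.0025 |

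**Step 3. Type I error.** Across the three primaries the bound is 3 × 0.05/m: 0.05 at m = 3, 0.021 at m = 7, 0.0075 at m = 20. It does not exceed 0.05 for any pre-fixed m of 3 or more.

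**Step 4. Power for one primary.** For every possible pair of event counts (i, j), 27 × 27 tables, compute the two-sided P value. Then power = Σᵢ Σⱼ Bin(i; 26, p₁) · Bin(j; 26, p₂) · 1{P(i, j) < 0.05/m}. For the plan's t-test on 0/1 data, t = (p̂₁ − p̂₂)/√(2s²/26) with s² = 26[p̂₁(1 − p̂₁) + p̂₂(1 − p̂₂)]/50 and 50 degrees of freedom.

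| Scenario | m = 3 | m = 6 | m = 7 | m = 20 |
|---|---|---|---|---|
| 31% vs 3%, pooled t-test | 64.6% | 52.7% | 51.1% | 37.3% |
| 31% vs 3%, Fisher | 51.1% | 37.3% | 37.3% | 24.8% |
| 10-point reduction, pooled t-test | 5.3–6.2% | 3.1–3.6% | about 3% | 1.2–1.4% |

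The 10-point row covers 18 vs 8, 21 vs 11, 31 vs 21 and 38 vs 28%. A normal approximation gives 62.4% at m = 3 and 49.9% at m = 7 for 31% vs 3%. The t-test loss is not smooth: power is still 64.3% at m = 5, so most of the drop falls between 5 and 6 tests, a step caused by the discrete data.

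**Step 5. Can the divisor decide a result?** Yes. Delirium in 9/26 vs 1/26 gives Fisher P = 0.0109. That is below 0.0167 (3 tests) but above 0.0083 (6) and 0.0071 (7).

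**Step 6. Holm over the three primaries.** Power for delirium at 31% vs 3%, pooled t-test, independent outcomes: 65.0% if the other two do not respond (30% in both arms) and 80% if all three show 31% vs 3%. Bonferroni over three gives 64.6% in both cases. The documents give 31% vs 3% for delirium only, so the second case is an unsupported assumption.

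**The case against.** **Another reading removes the power loss.** The Bonferroni sentence could mean adjustment within the primaries and, separately, within the secondaries. The primary threshold would then be 0.0167 and nothing would be lost to secondary tests. This stands: the text does not establish that the primary alpha depends on the secondary count. What it does establish is that two readings with different thresholds are both open.

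**One family over everything is legitimate.** Controlling error across all comparisons is conservative, not wrong. This also stands. A reader might infer that an unspecified Bonferroni inflates type I error, but step 3 shows that it does not when the count is fixed beforehand.

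**The loss is small on the plan's own assumption.** For a 10-point reduction it is 2–3 points, because power is already 5–6% at three tests. The fall from 65% to 51% rests on one earlier study's delirium result, which is not the planning effect. A reader should not take that fall as the plan's expected loss, nor think that repairing multiplicity rescues the trial.

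**The six cognitive instruments might seem to make eight primary tests** (six plus delirium and renal dysfunction). The documents do not support that count. The primary is named as an incidence and is to be expressed as a percentage, so three is the textual number. The missing rule for dysfunction matters only because the family of three needs it.

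**Examples near a threshold depend on the test.** With 8/26 vs 1/26 the pooled t-test gives P = 0.0096, which passes at 5 tests (0.0100) and fails at 6. Welch's version gives 0.0110 and already fails at 5, and the plan does not say which applies. The Fisher example in step 5 does not have this weakness.

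**Conclusion.** The concern holds in a limited form and should be corrected. The plan names Bonferroni but not the family or divisor. The primary threshold is 0.0167 on a per-family reading and 0.0071 or lower on the plain reading if mortality is tested and each named outcome is tested once. On the plain reading the power cost at 26 per arm is about 14 points for 31% vs 3% (65% to 51% with the pooled t-test; 51% to 37% with Fisher) and 2–3 points for a 10-point reduction. On either reading, a divisor not written down beforehand could be chosen after the data are seen.

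This rests on two-sided testing and on reading the 10% as percentage points. Any count above 7 is assumed. The sample size is the larger defect and this change does not repair it, though any re-sizing will need the fixed alpha that the change supplies.

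**What to change.** In Data Analysis, replace the Bonferroni sentence with:

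*Family-wise error of 0.05 (two-sided) is controlled across the three primary outcomes (delirium, cognitive dysfunction as one yes/no outcome, renal dysfunction) by the Holm procedure; secondary outcomes and mortality form a separate family, Holm-adjusted within it, and do not affect the primary thresholds.*

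State in the significance sentence that 0.05 refers to the adjusted P value. Fix the yes/no rule for cognitive dysfunction before data are seen, since the family of three depends on it, and list the members of the secondary family so that its own thresholds are defined.

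Holm is never less powerful than Bonferroni on the same family. Most of the gain comes from separating the families, and Holm adds little (65.0% vs 64.6%) if only delirium responds. Bonferroni over the three named primaries is an acceptable second choice.

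**Cost.** A few sentences and no new data. Error is controlled within each family rather than across both: the bound over both is 0.05 + 0.05 = 0.10, and with 3 and 4 independent tests under Bonferroni it is 1 − (1 − 0.05/3)³(1 − 0.05/4)⁴ = 0.096. Whether to go further and report the secondary outcomes, including those of Specific Aim 2, without significance claims is for the investigators to decide.
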